A crucial weakness of existing empirical studies comes from the operationalization of alcohol harm. With few exceptions,¹³ a vast majority of studies used a composite endpoint combining several causes of alcohol-attributable deaths or hospitalizations or even merging alcohol-attributable hospital admissions with deaths in a single outcome.^{6,9} While this strategy increases the statistical power to analyse rare events, composite endpoints are prone to misclassification bias by masking divergent underlying patterns and associations.¹⁴

Cause-specific analyses might shed light on different mechanisms driving the socioeconomic differences in overall alcohol-attributable harm, as well as opening potential avenues for policy interventions to reduce them. We will take advantage of a recently formed dataset covering the total Finnish population to explore associations between socioeconomic status and cause-specific alcohol-attributable events. An additional contribution to the literature will be reporting both relative and absolute inequalities in alcohol-attributable harm. Absolute differences have been rarely reported^{8,15} even though might be as relevant as relative differences because, from a pragmatic standpoint, they are more feasible to reduce.¹⁶

The study will aim to (1) examine the relative and absolute socioeconomic differences in cause-specific alcohol-attributable hospital admissions and deaths; (2) describe the geographical differences in cause-specific alcohol-attributable hospital admissions and deaths; and (3) quantify the relative contribution of each specific alcohol-attributable cause to the overall alcohol-attributable harm.

Methods

Study design and setting

The study is a nationwide population cohort study of the entire Finnish population from January 1, 2016, to 28 February 2020. Individuals in Finland are assigned a unique identifier at birth or immigration and used in all public and private administrative records. We will use the unique identifier to link socioeconomic information with hospital admissions and deaths.

Participants

Participants will be all permanent residents (see below for a definition) aged 25 and over in Finland by the last day of 2015 and without an alcohol-attributable hospital admission during the past three years (January 2013-December 2015). The age limit of 25 was considered because younger adults might have their education ongoing and their income and occupational class may not reflect their true socioeconomic standing. We will exclude residents with prior hospital admissions during the past three years to reduce the risk of reverse causality.

Data sources

We will use data from the FOLK database (basic module, module for Household Dwelling Unit and module of Degree/Qualifications) maintained by Statistic Finland.¹⁷ The FOLK database contains individual-level data on income, education, family, degrees and qualifications and cohabitation. Educational level data comes from the Register of Completed Education and Degrees. Income data derive from Statistics Finland's income distribution statistics and personal taxation data. Occupation data derives from a combination of sources from registers of employment relationships, statistics on wages and salaries and data on enterprises.¹⁸ We will use data on hospital admissions from the Finnish Care Register for Health Care (HILMO) which covers all hospital admissions in public and private inpatient hospitals in Finland. We will use mortality data from the Causes of Death register administered by Statistics Finland.

Outcomes

The outcome will be cause-specific alcohol-attributable hospital admissions and deaths. We will include any wholly-attributable cause (i.e. an attributable fraction of 1) included in the main and secondary causes of hospitalization as well as the underlying and contributory causes of death. Drawing on national reports and previous studies,¹⁹ we will use the following International Classification of Disease (ICD) codes:

ICD-10 code	Diagnosis
F10.0-1	Alcohol intoxication
F10.2	Alcohol dependence
F10.3-9	Psycho-organic syndrome caused by alcohol
K70	Alcoholic liver disease
K85.2, K86.0	Pancreatic diseases caused by alcohol
K29.2	Gastritis caused by alcohol
I42.6	Alcoholic cardiomyopathy
G312, G4051, G621, G721	Degeneration of the nervous system due to alcohol, Epileptic seizures related to alcohol, Alcoholic polyneuropathy, Alcoholic myopathy
T51, X45	Alcohol poisoning

We will exclude perinatal causes (O354, P043, Q860) as they are impossible in this study population.

Hospital admissions. We will define hospital admission as any event including at least one overnight stay in inpatient care. Patients having two hospital admissions in two hospitals with overlapping dates will be considered as a single hospital admission. We will include admissions where the main or secondary causes are attributable to alcohol. Given we are examining cause-specific alcohol-attributable events, we defined criteria to attribute the cause in case of overlapping or multiple alcohol-attributable ICD-10 codes. For hospital admissions with more than one alcohol-attributable cause, we will consider the main cause as the hospitalization cause. In hospital admissions with more than one alcohol-attributable ICD-10 code, we will consider the main cause as the hospitalization cause. If there are several alcohol-attributable main causes, we will consider first the complexity of the inpatient provider (provider code in the HILMO dataset). In the case of ties by complexity, we will consider the longest stay. We will not include outpatient visits, day-hospital treatments or emergency care visits.

Deaths. We will define alcohol-attributable deaths as any death where an alcohol-attributable cause is either the underlying, immediate, intermediate or contributory cause of death.

We will follow participants until the first hospital admission, death or end of follow-up. We will restrict follow-up until February 28, 2020, to avoid confounding due to the COVID-19 pandemic.

Exposure

The exposure of interest is socioeconomic status. Our main proxy of socioeconomic status will be disposable household income. In addition, we will use educational level and occupational class. All exposures are measured by the last day of the calendar year (2015). We will calculate equivalised disposable income by adjusting the combined disposable income of a household to the household size unit using the OECD-modified equivalence scale. The income measure in this study is the sum of wage and salary earnings, self-employment income, property income and current State transfers after subtracting direct taxes and social security contributions. For persons in non-dwelling units (e.g. living in institutions, homeless, abroad or registered as unknown) we will consider their personal net income without equalization. We will also run sensitivity analyses excluding those participants.²⁰

We will categorise educational level according to the highest qualification completed degree into lower secondary education or less (missing data on education), upper secondary education or post-secondary (levels 3 and 4) and or short-cycle tertiary education, Bachelor's or equivalent level and higher (levels 5, 6, 7 and 8). Due to restrictions in available data, we do not have information on individuals' educational attainment if it is less than lower secondary education. Because of this, we do not know the proportion of the study population the information is truly missing.

We will categorise occupational class into manual workers (codes 51, 52, 53, 54, 59), self-employed persons (codes 10 and 20), lower-level employees (codes 41, 42, 43 and 44) and upper-level employees (31, 32, 33, 34), students, pensioners and those unemployed. This classification is created by Statistics Finland and derives from the person's main type of activity, occupation, occupational status and industry. Persons outside the labour force are assigned the same class as the reference person in the household. For persons in non-dwelling units, given there is no reference person, we will treat this group as a separate category of occupational class. The [Supplementary Appendix](#) includes a detailed description of how these variables are created.

Confounders

We will control for sex, age, marital status, and mother tongue. We will categorise sex as male or female. We will categorise marital status as unmarried, married, in a registered partnership or separated, divorced or divorced from a registered partnership or widowed or widowed from a registered partnership. We will categorise mother tongue as Finnish, Swedish and other.

Bias

Confounding bias. We will reduce the risk of confounding bias by adjusting for potential confounders that are associated with the exposure and the outcome. Our data derives from national registries and provides excellent coverage of observed sociodemographic characteristics. However, we do not have data on behavioural factors, such as tobacco or

alcohol use, or personality traits. The risk of residual confounding can only be attenuated but not be fully removed in our study design.

Information bias. Information from national registries is not subject to recall or social desirability bias. Education data can be subject to measurement error due to missing information for lower levels of education. This can be more severe for immigrants because the Register of Education and Completed Degrees might not register degrees obtained abroad. Statistics Finland has been able to obtain information on more than 13.000 degrees obtained in Nordic countries and 26.000 degrees in other countries.²¹ Nonetheless, the educational attainment of foreigners who studied abroad might be underestimated. In sensitivity analyses, we will re-run the analyses excluding foreigners. We anticipate, however, that this will have a negligible effect on our estimates, as foreigners represent a small proportion of the population. The Finnish economy is highly formalized and informal employment is estimated at 1-3% of those employed. These include freelancers, own-account workers in the informal economy, contributing family workers and grant recipients. Therefore, income and employment statistics include 97-99% of the employed population.²² Statistics Finland also has routine procedures to assess the quality of registry data, starting from the studies carried out to compare census with survey data in the 1980s and from employment surveys conducted regularly.¹⁸ The quality of Finnish registry data is, hence, subject to minimal information bias.

Selection bias. Our data comes from the total Finnish population and, therefore, is not subject to selection due to participation. The data includes permanent residents in Finland, defined as all Finnish nationals and foreign nationals who have a legal domicile in Finland and intend to stay (or have stayed) for at least one year. This excludes foreign nationals living in Finland for less than a year, asylum seekers who have not been granted a legal domicile and temporary migrant workers (e.g. cherry pickers and construction workers), and Finnish nationals living temporarily abroad.²³

Selection bias can also arise due to loss of follow-up, although in Finland deaths missing a death certificate are extremely rare (about 0.2%).²⁴ We consider the risk of selection bias due to loss of follow-up relatively small.

Quantitative variables

All variables included in the analyses are categorical.

Ethical approval

The use of administrative records does not require ethical approval in Finland. All data used was pseudonymised and linked by Statistics Finland and will be analysed in a protected remote access system FIONA. We will comply with Finnish regulations established under the National Statistics Act and the supplementary National Data Protection Act as well as with the General Data Protection Regulation from the European Union.²⁵ Permission for data usage and linkage was given to the Finnish Institute for Health

and Welfare as part of the Compensation Criteria and Evaluation of Provinces project (permission K/3184/07.03.00/2022, U1098_a19)

Statistical methods

We will use the relative index of inequality (RII) and the slope index of inequality (SII) to compare and quantify the socioeconomic gradient in cause-specific alcohol-attributable hospital admissions and deaths. We will use regression models for estimation with individual time-to-event data: Cox proportional hazards models for relative inequalities and Aalen additive hazard models for absolute inequalities.

For the RII, we will fit the following Cox proportional hazards model,

$$(1) \quad \lambda(t | G = k) = \beta_0(t) \exp\{\beta x_{(k)} + \beta(t)L_i\}$$

Where G represents the socioeconomic group and we approximate the rank of each person in the k th socioeconomic group by the rank $x_{(k)}$ defined as the percentage of the population in strictly higher groups plus half of the percentage in group k , and L_i denotes a vector of covariates (sex, marital status, etc.).²⁶ This method allows us to incorporate the whole socioeconomic gradient, instead of comparing the lowest and highest socioeconomic groups. The estimate of \widehat{RII} is equivalent to $\exp(\widehat{\beta})$.²⁶

We will use age as the timescale, as age is strongly correlated with the risk of hospitalization and mortality.²⁷ We will report regression estimates as hazard ratios (HRs) with 95% confidence intervals (CIs). Given we studied cause-specific events, deaths due to other causes represent competing risks. To account for this, we will use cause-specific hazards by censoring other-cause events to the time of the death by other causes or the end of follow-up on February 28, 2020. We will examine the proportional hazards assumption globally and for each covariate using scaled Schoenfeld residuals.²⁸

For the SII, we will fit age-standardized Aalen additive hazard models,

$$(2) \quad \lambda(t | G = k) = \alpha_{0s}(t) + \alpha_s x_{s(k)} + \alpha(t)L_i$$

where the age standardization is the weighted sum of estimated age-group-specific indices. For this we will fit separate additive hazard models within each age-group $s = 1, \dots, S$. The estimate of the \widehat{SII} is equal to $\widehat{\alpha}$.

Same as before, we will use age as the timescale and report regression estimates as events per 100,000 person-years with 95% confidence intervals. We will report cause-specific hazards to account for competing risks.

In practice, we will run a model for each cause-specific condition (nine models in total) separately for alcohol-attributable hospital admissions and alcohol-attributable deaths.

For objective 2, we will run stratified analyses by hospital districts and Åland (n =21). We will report the RII and SII by region in plots or maps in order to obtain a visual representation of both the degree of between-region inequalities and geographical patterns in the distribution of alcohol-attributable harm. Considering we might not have enough statistical precision to obtain informative estimates for regional differences for all cause-specific outcomes, we will report overall alcohol-attributable admissions and deaths (separately) and, in the Supplementary Appendix, the most common specific causes.

For objective 3, we will quantify the relative contribution of each specific cause by dividing the SII for the specific cause by the overall SII for either hospital admission or death and multiplying by 100.

We will run the same Cox proportional hazards and additive hazards models for educational level and occupational class. However, given these are categorical variables with an unclear ordinality and the relationship with the outcome might not be linear, we are not able to estimate the RII or SII. Instead, we will use the standard approach of comparing the hazard ratio and additive hazard comparing the category to a reference group (highest education and upper-level employees, respectively).

Missing data for covariates in the FOLK datasets is minimal. Sex, age, marital status and mother tongue do not have missing data. We described above how we will handle missing data for education. For models using income and occupation, we will use multiple imputation using chained equations to address missing data.

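### One follow-up rule serves two separately modelled outcomes; applied as written to the death models, it stops the clock at the first alcohol-attributable admission

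*Combined protocol and SAP*

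**What the plan says.** Under Methods, Outcomes, the protocol defines admissions, then deaths, and then gives one rule after both: "We will follow participants until the first hospital admission, death or end of follow-up". The end of follow-up is 28 February 2020. The rule does not say which stop applies to which outcome.

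An alcohol-attributable death is "any death where an alcohol-attributable cause is either the underlying, immediate, intermediate or contributory cause of death".

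Under Statistical methods, one model is fitted per cause, nine in all, "separately for alcohol-attributable hospital admissions and alcohol-attributable deaths". On competing risks, that section says that "deaths due to other causes represent competing risks" and that cause-specific hazards will be obtained by "censoring other-cause events to the time of the death by other causes or the end of follow-up on February 28, 2020". Admission does not appear there.

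Objective 3 expresses each cause's contribution by "dividing the SII for the specific cause by the overall SII for either hospital admission or death", times 100.

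The introduction criticises earlier work for "merging alcohol-attributable hospital admissions with deaths in a single outcome".

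**The concern.** Cox and Aalen models need an event date and a censoring date for every person and every outcome. The plan gives one set of stops for two outcomes, and admission is among them. In an admission model, the first qualifying admission is the event, so stopping there is correct. In a death model, an admission is neither the event nor a stated competing risk, yet the sentence read as written ends follow-up there.

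The death models would then estimate the hazard of alcohol death without a prior in-study alcohol admission. That is a coherent quantity, but it is not the outcome that aim 1 announces. Because people with an alcohol-attributable admission in 2013–2015 are already excluded at baseline, these models would describe alcohol deaths only among people with no such admission from January 2013 onwards.

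A second gap concerns the cause-specific admission models. It is not stated whether a first admission for a different alcohol cause ends follow-up for the cause being modelled.

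**Working it through.** The plan has no sample size, power or event count to reproduce. The check is a comparison of the text, followed by algebra to see whether the consequence can be sized or signed.

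**1. Stops that the text gives for a death model**

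| Source | Admission | Other-cause death | 28 February 2020 |
|---|---|---|---|
| Outcomes, follow-up sentence | yes | yes (any death) | yes |
| Statistical methods, censoring sentence | not listed | yes | yes |

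The two sources give different risk sets, and no other section says that death models either stop at an admission or continue past it.

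**2. Would a planned analysis reveal the difference?** The plan has three candidates: excluding people in non-dwelling units (Exposure), excluding foreigners (Information bias), and separating main or underlying causes from secondary or contributory ones (end of Statistical methods). None changes the stopping rule.

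**3. Effect on the death SII and RII.** This simplification ignores age and covariates. At income rank x (higher x means lower income under the plan's definition), let

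- d0(x) = alcohol-death rate before any in-study alcohol admission,
- d1(x) = alcohol-death rate after one,
- p(x) = share of full-follow-up person-time that falls after one.

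Then

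- stopped at admission: r_stop(x) = d0(x);
- full follow-up: r_full(x) = [1 − p(x)]·d0(x) + p(x)·d1(x);
- difference: r_full(x) − r_stop(x) = p(x)·[d1(x) − d0(x)];
- ratio: r_full(x) / r_stop(x) = 1 + p(x)·[d1(x)/d0(x) − 1].

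The SII changes by the slope of the difference over x. If admissions are more common at low income, raise the risk of alcohol death, and mortality after admission does not fall steeply towards low income, the stopped SII is too low. If mortality after admission does fall steeply enough, the sign reverses. The RII changes according to whether the ratio rises or falls with x, so it can move either way, and not necessarily in the same direction as the SII.

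The documents give no value for p, d0 or d1, or for their gradients. The only usable input is the maximum follow-up: 1 January 2016 to 28 February 2020 is 1,461 + 59 = 1,520 days, and 1,520 / 365.25 = 4.16 years. That alone fixes neither size nor sign.

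**4. Objective 3, deaths.** Write SII_c for cause c under the stopped rule and Δ_c for its change under full follow-up. The share moves from SII_c / ΣSII to (SII_c + Δ_c) / Σ(SII + Δ). If Δ_c / SII_c is the same for every cause, the shares do not change. They change only if causes differ in how often, or with what income gradient, an admission precedes death. The documents do not say.

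**5. Objective 3, admissions.** If first means the first admission for any alcohol cause, and each admission is assigned to one cause, all cause-specific models share one risk set and their events add up to the overall events. If first means the first admission for the modelled cause, one person can be an event in several models but only once in the overall model. Numerator and denominator then count different things, and the shares need not sum to 100%.

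**The case against.** The strongest reply is that the sentence is ordinary shorthand to be read outcome by outcome: admission models end at the admission, death models at death, and both at the closing date. The separate paragraphs for admissions and deaths, the separate models, and the introduction's criticism of merging the two all fit that reading, and under it the death models lose nothing. This stands as a plausible account of intent. It is not written down, and a pre-specified plan should not leave event and censoring dates to inference.

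It is also fair to say that the censoring sentence in Statistical methods explains how competing risks are handled and does not claim to list every end of follow-up. Its silence on admission is therefore not an opposing rule. What remains is that the two places have not been aligned.

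Three stronger readings are tempting, and the documents do not support them.

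- *Any overnight stay ends follow-up.* A reader might infer this from "We will define hospital admission as any event including at least one overnight stay in inpatient care", since the follow-up sentence has no alcohol qualifier. But the protocol uses the bare term as shorthand. The Participants section states the baseline exclusion first with the alcohol qualifier and then without it, and the objective 3 formula omits the qualifier where only alcohol-attributable admissions can be meant.
- *The rule contradicts the definition of an alcohol-attributable death.* That definition concerns where the alcohol cause sits on the death record, not when the death occurs. Missing the deaths after an admission is a consequence of the follow-up rule, not a contradiction in wording.
- *The death gradient will be underestimated.* The algebra above shows that the direction depends on quantities the documents do not give.

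**Conclusion.** The point holds as an unresolved follow-up rule that should be settled before analysis. Applied as written, the death models omit alcohol deaths after an in-study alcohol-attributable admission, which answers aim 1 less well than full follow-up would. The documents do not show that the analysts intend this. The conclusion rests on reading admission in that sentence as alcohol-attributable admission, in line with the protocol's usage elsewhere. The size and direction of any effect on the death RII, the death SII and the objective 3 shares cannot be determined from the documents; any figure would rest entirely on assumed rates. The case for acting is that the rule governs every death estimate, no planned analysis would reveal its effect, and the correction is cheap.

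**What to change.** Replace the single sentence under Outcomes with a rule for each outcome.

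- **Death models:** follow to alcohol-attributable death; censor at other-cause death or 28 February 2020; do not stop at an admission.
- **Admission models:** follow to the first alcohol-attributable admission; censor at death or 28 February 2020; state whether first means any alcohol cause or the cause being modelled. Use the same definition in the numerator and denominator of objective 3.

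Then align the censoring sentence in Statistical methods with these rules.

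The cost is minor: a few sentences of text, and separate event and censoring dates for each outcome, built from the hospital admission and cause-of-death registers already named under Data sources. No new data are needed.

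### Follow-up is not censored at emigration, so time after leaving Finland counts as event-free for the hospital-admission outcomes

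*Combined protocol and SAP*

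**What the plan says.** Under Methods, Outcomes, the paragraph after the definition of deaths sets the follow-up rule: "We will follow participants until the first hospital admission, death or end of follow-up". Statistical methods describes the cause-specific analysis as "censoring other-cause events to the time of the death by other causes or the end of follow-up on February 28, 2020". Neither sentence mentions emigration or loss of permanent residence, and no other section adds it.

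The design is a "nationwide population cohort study of the entire Finnish population from January 1, 2016, to 28 February 2020". Residence is established once, at entry: "Participants will be all permanent residents (see below for a definition) aged 25 and over in Finland by the last day of 2015". Data sources states that the hospital register covers public and private inpatient hospitals in Finland. Deaths come from the Causes of Death register, and the protocol does not say whether that includes deaths abroad.

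The Selection bias paragraph addresses loss to follow-up with one figure, a percentage: "Selection bias can also arise due to loss of follow-up, although in Finland deaths missing a death certificate are extremely rare (about 0.2". It then judges the risk to be relatively small.

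The text on people abroad at baseline is not consistent. The Exposure section says: "For persons in non-dwelling units (e.g. living in institutions, homeless, abroad or registered as unknown) we will consider their personal net income without equalization". The Selection bias paragraph lists "Finnish nationals living temporarily abroad" among those the data exclude. The Income section of the Supplementary Appendix gives a parallel list of people without a household dwelling unit and does not name people abroad.

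**The concern.** A person who emigrates in, say, 2017 can have no admission recorded in the Finnish register afterwards. Under the written rule that person still contributes time at risk until death or 28 February 2020. This time enters the Cox risk sets, and it enters the person-years behind an SII reported per 100,000 person-years. It is immortal with respect to admissions by construction.

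The plan's reassurance does not reach this problem. Completeness of death certificates says how well recorded deaths are documented. It does not say how many people left the country, and it has no bearing on admissions. The gap is therefore more than an unwritten routine detail: the plan raised loss to follow-up and answered it with a figure for something else.

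At stake are the level of the admission rates and, if emigration varies with income, the size of the gradients that the study exists to measure.

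**Working it through.** The plan states no emigration rate, event count or sample size, so it has no figure of its own to reproduce. The check is a reading of the rules plus an illustration of size.

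**Reading.** Exit events under Outcomes: admission, death, end of follow-up. Censoring under Statistical methods: death from other causes, or 28 February 2020. Residence is checked only at the end of 2015, and admissions are seen only in Finland. Together these mean that admission-free time after emigration is counted but cannot be observed.

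**Follow-up length (from the documents).** 1 January 2016 to 28 February 2020 is 1,520 days; T = 1,520 / 365.25 = 4.16 years.

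**False person-time (rates assumed).** With a constant emigration rate e per year and no return, the observable fraction of counted time is g(e) = (1 − exp(−eT)) / (eT), and the false share is 1 − g(e). For e = 1%, eT = 0.0416, g = 0.9795 and the false share is 2.05%.

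| e per year | g(e) | False share |
|---|---|---|
| 0.2% | 0.9958 | 0.42% |
| 0.4% | 0.9917 | 0.83% |
| 0.5% | 0.9897 | 1.03% |
| 1% | 0.9795 | 2.05% |
| 2% | 0.9595 | 4.05% |
| 4% | 0.9212 | 7.88% |

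**Effect on a low-versus-high income comparison.** Assume a true rate ratio of 5, with the high-income rate set to 1, so the true gap is 4.00. The observed ratio is 5 × g(low) / g(high), and the observed gap is 5 × g(low) − g(high).

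- Both groups at 0.5%: ratio 5.00; gap 4 × 0.9897 = 3.96.
- Low 1%, high 0.2%: ratio 5 × 0.9795 / 0.9958 = 4.92 (1.6% too low); gap 4.8975 − 0.9958 = 3.90.
- Low 0.2%, high 1%: ratio 5 × 0.9958 / 0.9795 = 5.08 (1.7% too high); gap 4.979 − 0.9795 = 4.00.
- Low 0.2%, high 2%: ratio 5 × 0.9958 / 0.9595 = 5.19 (3.8% too high); gap 4.979 − 0.9595 = 4.02.

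**Ten income deciles.** Assume a log-linear true RII of 5 and a mean rate of 300 per 100,000 person-years, which gives a true SII of 463.0. A Poisson fit for the RII and a linear fit for the SII, applied to the diluted rates, give:

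- uniform emigration at 0.5%: RII 5.00, SII 458.2;
- 1% in the top decile and 0.2% elsewhere: RII 5.03, SII 462.2.

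The level of the rates always falls. The ratio can move either way, and the gap usually falls but can rise slightly.

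**The case against.** The strongest defence is that the effect is small and partly covered. Several parts of that stand.

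- A reader might infer that the SII must be too low. It need not be: with emigration concentrated at high income, the illustrated gap is 4.02 against a true 4.00.
- A reader might infer that emigration differing by age or mother tongue biases the RII. Age is the timescale and mother tongue is adjusted for, so differences along those lines alone are largely absorbed. What matters is a difference by income that remains after them.
- A reader might apply 2% to 4% per year to the whole lowest-income group, which would understate the low-versus-high ratio by 3.6% to 7.5% if the highest group left at 0.2%. Nothing in the documents supports such rates for a whole income group. Suppose instead that 20% of the lowest group left at 4% and the rest at 0.2%. The false share there is 0.2 × 7.88 + 0.8 × 0.42 = 1.9%, and the ratio is understated by about 1.5%.
- A reader might extend the point to deaths. The documents do not say that deaths abroad are missed, so this stays open.
- A reader might conclude that the plan knowingly enrols people living abroad. The mention sits in a list of examples, the eligibility text points the other way, and a sensitivity analysis already removes everyone in non-dwelling units. This is a wording conflict to reconcile.

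What does not stand is that the sensitivity analyses close the gap. Removing people in non-dwelling units at baseline does nothing about those who emigrate later. Removing foreigners, planned because of education measurement error, leaves in every Finnish national who emigrates.

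**Conclusion.** The concern holds for the admission outcomes. As written, the rule counts person-time after emigration as event-free, and the stated reason for regarding loss to follow-up as small does not measure emigration.

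Admission rates are understated, by about 0.4% to 2% of person-time at assumed emigration rates of 0.2% to 1% per year, and by 4% to 8% only within subgroups leaving at 2% to 4%. The direction of any bias in the RII and SII cannot be told from the documents. Uniform emigration leaves the RII as it is and lowers the SII by about the false share (463.0 to 458.2, or 1.0%, at 0.5% per year).

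These sizes rest on constant emigration rates, no return, and an assumed RII and mean rate. They are illustrations and not estimates for Finland. Confidence is high in the omission itself and low in its size. The change is worth making because it corrects a stated rule and removes a bias of unknown direction from the main measures.

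**What to change.** 1. Amend the follow-up rule under Outcomes, and the matching sentence under Statistical methods, so that follow-up ends at the first event, death, emigration (loss of permanent residence) or 28 February 2020. If only annual residence status is held, censor at the last 31 December on which the person belongs to the permanent-resident population.
2. Reconcile the Exposure section's "living in institutions, homeless, abroad or registered as unknown" with Participants, the Selection bias paragraph and the Appendix list. Keep anyone not resident on 31 December 2015 out of the main risk set.
3. State whether the Causes of Death register includes deaths abroad for this cohort.
4. In the Selection bias paragraph, replace the death-certificate argument with the number censored for emigration by income group.

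The cost is a few sentences and a small loss of person-time. A residence-status variable may have to be added to the linked data. The documents list three FOLK modules and a specific data permission but do not say whether such a variable is already held, so the administrative effort is uncertain.
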